***Post Treatment**

Demographic Measures. Age, race, gender, marital status, education, employment status, travel time, cell and smartphone use will be collected from each participant at baseline.

Physical Activity-Related Measures. The Stanford 7-day Physical Activity Recall (PAR) Scale (Sallis et al., 1985) will be used to quantify total engagement in physical activity at baseline, post-quit, 3-month follow-up, and 6-month follow-up. During the mobile monitoring period (baseline, treatment, and 1-week post-treatment) mean daily steps will be collected remotely and tabulated each week.

Smoking-Related Measures. The Fagerström Test of Nicotine Dependence (FTND; Heatherton, Kozlowski, Frecker, & Fagerström, 1991), Minnesota Nicotine Withdrawal Scale (Hughes &

Hatsukami, 1986), and a general smoking history questionnaire (e.g., number of cigarettes smoked/day, age of first smoking, number of previous quit attempts, living with a smoker) will be used to measure smoking behaviors. Participants will be asked to respond to several questions to determine if he/she has contraindications to receive smoking-cessation medications.

Quality of Life. Physical- and mental-health quality of life will be measured at baseline, post-treatment, and at 3- and 6-month follow-ups using the Short Form 36 Health Survey (Ware & Sherbourne, 1992).

Self-Efficacy, Readiness to Change, and Social Support. A single item (“How confident are you that you will be able to quit smoking?” 1 = “Not at all confident” to 4 = “Very confident”; Shiffman et al., 2000) will be used to measure global self-efficacy for quitting smoking at baseline, post-treatment, 3-month follow-up, and 6-month follow-up. The use of a global measure of SE is supported by previous studies in which multiple-item SE questionnaires formed a unifactorial construct (Baer, Holt, & Lichtenstein, 1986). The Readiness-to-Change Questionnaire (RCQ; Rollnick, Heather, Gold & Hall, 1992), which is designed to assess attitudes toward quitting smoking (Heather, Rollnick, & Bell, 1993), will also be administered at those time points. Self-efficacy for taking NRT and bupropion as prescribed will be assessed on a 10-point Likert scale. Self-efficacy for increasing physical activity will be similarly assessed on a 10-point Likert scale. Social support will be assessed using a single item used in the NIH PROMISE study (Williams et al., 1992): “Do you have someone you feel close to, someone you can trust and confide in?”

Affect and Physical Vigor. Positive and negative affect and physical vigor will be quantified at baseline, each week during the 6-week intervention and monitoring period, and at post-treatment. Positive and negative affect will be measured using 2 Likert-scale items: “During the past week, to what extent have you felt positive (e.g., happy, proud, excited)/negative (e.g., angry, irritable, upset)?” Responses range from 1 (“Very slightly or not at all”) to 5 (“Extremely”). Physical vigor will be measured using 5 items from the Shirom-Melamed Vigor Measure (Shirom, 2003). Participants will be prompted to indicate how often they have felt each of the following during the past week: “I feel full of pep,” “I feel I have physical strength,” “Feeling vigorous,” “I feel energetic,” and “Feelings of vitality”, with responses ranging from 1 (“Never or almost never”) to 7 (“Always or almost always”).

Measures of Treatment Acceptability. Participants’ satisfaction with the intervention will be assessed via an in-depth interview, including 17 Likert-scale survey items, at the end of treatment. These items will assess: 1) reactions to the topics discussed and skills reviewed; 2) comfort with the counselor; 3) opinions of the materials used in session and homework (e.g., participant workbook); 4) overall satisfaction with the intervention at that point in time; and 5) comfort with the mHealth applications (mCM for smoking cessation and physical activity and supportive messaging).

Measures of Treatment Feasibility and Adherence. Feasibility of participant retention will be assessed by detailed tracking of attendance at each treatment session. Measures will include number of counseling sessions completed, the number of missed or cancelled appointments, and the proportion of participants who withdraw/drop out or are lost to follow-up. Participants who withdraw from treatment will be contacted to elicit feedback on their reasons for dropping

out. Feasibility of the use of the mHealth applications will be assessed by tracking: 1) the proportion of required videos uploaded using the mCM app; 2) participants use of the text-messaging keywords; 3) information regarding lost or stolen cell phones; and 4) participants' use of and comfort with the mHealth apps at the beginning and end of the intervention. We will also assess the number of participants who have a) mobile smart phones and b) current subscription to and size of mobile data plans (which will inform budgeting for a larger trial).

Medication adherence to NRT and bupropion will be assessed. Individuals who are optimally adherent have been found to be more than twice as likely (52%) to be abstinent at 6 months than were those with lower adherence (25%; Catz et al., 2011). Optimal adherence will be defined as using > 80% of their NRT and bupropion. The primary self-report measure of adherence will be the number of days NRT (and bupropion if prescribed) are used during the study period. Participants will also complete the Morisky Adherence Questionnaire (Morisky, Green, & Levine, 1986). This 8-item questionnaire is a general adherence measure that produces unintentional and purposeful non-adherence subscales. The questionnaire has been validated with smokers as an adherence screening measure (Toll, McKee, Martin, Jatlow, & O'Malley, 2007) and as a post-treatment measure of adherence (Catz et al., 2011). Days of medication use will be recorded at each telephone session and follow-up during treatment, post-treatment and 3- and 6-month follow-ups (for bupropion).

Smoking-Cessation Outcome Measures and Biochemical Verification. Our choice of primary and secondary smoking endpoints follows recommendations by the Society of Research on Nicotine and Tobacco (SRNT; Hughes et al., 2003). Self-reported and bio-verified prolonged abstinence at the 3- and 6-month follow-ups will be the primary endpoints. Prolonged abstinence will exclude tobacco use in the first 2 weeks following the quit date (Hughes et al., 2003). Self-reported prolonged abstinence will be verified by cotinine assay. CO and saliva samples will be collected from participants who report prolonged abstinence at each follow-up. Saliva samples will be sent to the Duke University Nicotine Research Program to be analyzed for the presence of cotinine using a standard cut point of 10 ng/ml to determine abstinence. A blind sample of 5% will be rerun to assure test accuracy of saliva samples. Secondary smoking outcomes will include 7- and 30-day point prevalence abstinence at each assessment, where abstinence is defined as no tobacco use in the prior 7 or 30 days respectively. Additionally, participants will be asked if they have made one or more quit attempts in each follow-up period using a time-line follow back method (Lewis-Esquerre et al., 2005). We have recent experience using this method to assess daily smoking behavior (Carpenter et al., 2015).

Potential Risks

There is a risk of discomfort or distress in answering questions on the study measures. However, distress and discomfort related to questionnaire completion is usually temporary and well-tolerated. Risks also include discomfort related to quitting smoking. Quitting smoking may cause difficulty concentrating, poor sleep, increased appetite, anxious or depressed mood, and craving for cigarettes. Participants will be offered NRT, and there are risks associated with the use of NRT. Minimal risks associated with wearing a nicotine patch include skin irritation, dizziness, lightheadedness, increased heart rate or blood pressure, nausea or vomiting. If a participant indicates a contraindication to NRT (e.g. uncontrolled hypertension), medical clearance for NRT will be sought from the participant's primary care physician and/or the study physician. If a participant with a seizure disorder, history of or current hepatitis and/or cirrhosis, renal

impairment, and/or uncontrolled diabetes wishes to enroll in the study, he/she will not receive contraindicated medications.

Participants who are medically eligible will also be prescribed bupropion SR. Risks of bupropion use include dry mouth, insomnia, nausea, constipation, headache, shakiness or jitteriness, skin rash, sweating, allergic reaction, change in appetite, weight loss, dizziness, tremor, thinking abnormally, hot flashes, worsening depression or suicidal thoughts and behavior, and ringing in the ears. At the highest dosage of bupropion to be used in this study, seizures occurred in 1 out of every 1000 (0.1%) who took this drug. Participants are informed that they are not required to take bupropion, and will be allowed to participate in the study if they refuse to do so.

The risk of doing moderate exercise is low, and may be associated with risk of injury, falls, fainting, dizziness, or muscle soreness. There is even the risk of sudden death or stroke. To minimize these risks during exercise, participants will be instructed to exercise at a comfortable level and to never push themselves to a point beyond where they feel safe. Participants will also be monitored and instructed to report symptoms such as unusual shortness of breath, dizziness, tightness or pain in the chest or arms, skipping heart beats, numbness, loss of balance, nausea, or blurred vision.

There is a potential risk associated with the loss of confidentiality of study data. Specifically, collection and transfer of videotaped carbon-monoxide monitoring have risks with regards to privacy and confidentiality. Please see "Protection Against Risk and Data Security Measures" for details on reduction of risk with regards to the proposed videotaping.

Protection Against Risk and Data Security Measures

While participants may benefit from quitting smoking and increasing physical activity, there are no guaranteed benefits to the individual participant and no immediate benefits of the proposed research to others. There are potential benefits to others from the information generated that potentially will be helpful in developing new combined treatments for smoking and physical activity. In our opinion, the anticipated benefits of this study outweigh the potential risks.

The study is completely voluntary and participants are informed that they are free to refuse to answer any items on the questionnaires or questions from the interview that they do not wish to answer. They are also informed that they are free to decline participation in any procedure and can withdraw from the study at any time.

Potential risks will be minimized by carefully screening potential participants according to the inclusion/exclusion criteria, closely monitoring symptom levels, and following established laboratory procedures associated with participant safety.

We have included at the end of this full protocol a data flow diagram that describes data movement within the study. We will be providing the study phones to participants for the course of the monitoring period and will retrieve them at the conclusion of monitoring. Phones will be equipped with the STEP UP mobile app developed by our team, and with Fitbit Flex 2 App to allow data to be transferred to Fitbit's servers. Their API states that they use OAuth 2.0 to authenticate API requests and that must be done over secured (SSL/TLS) connections.

Participant data that is updated to Fitbit's servers will be deidentified, and no actual participant information will be provided to Fitbit in order to set up the accounts.

On the smart phones, we will restrict access to the following applications: internet browsers, installation of apps, deletion of apps, and in-app purchases. We will prevent access to music, podcasts, movies, TV shows, apps, and other websites. We will prevent ability to change the following: accounts, cellular data use, background app updates, location services, contacts, calendars, reminders, photos, Bluetooth sharing, microphone, Twitter, Facebook, and advertising. We will have the ability to remotely wipe the phones if they are not returned. We will encourage participants via consent to only enter information on the phone that they are comfortable with sharing with the entities listed below.

Regarding mobile information security, we have taken care in previous projects using similar methods and technology to develop procedures to limit the risk of breach of confidentiality and privacy. For example, the smart phone is programmed such that a staff member will set up the telephone and enter the participant's code into the phone. When uploading a video, participants upload directly from the phone to an approved website that has been vetted by Duke's information security officers, and the phone programming ensures that the video is uploaded into the correct participant's area of the website. This ensures that study participants' data is stored in the correct place, and that study participants cannot view any other participants' data. Participants are asked to review their videos before posting, and they can choose not to upload any video that they do not wish to upload for any reason. In previous studies that have been run using this methodology, we have had no participant complaints regarding issues of privacy and confidentiality related to use of the smart phone videotaping procedures. In order to enhance participants' privacy, we will restrict access to several of the telephone's ancillary applications, and we have the ability to remotely delete data from any phones that are not returned to the study team.

For the study's website, we will use shared server space provided by InMotion Hosting, Inc (website www.[name].com). We will be using AES-256-CBC encryption with SHA1 for message authentication and RSA as the key exchange mechanism. The video recordings will be collected on devices that are FIPS-140-2 compliant. The data at rest at InMotion Hosting is AES-256 encrypted at rest, and the data being transferred are encrypted at transfer (AES-256). Data will be unencrypted only by study staff members who have access to the secured server at InMotion Hosting; the encryption key is held only by our staff. This will ensure all video uploads and data that the participant sends over the internet via their phones will only be transferred over encrypted network connections, essentially nullifying the possibility of someone gaining access to the video before it reaches our server. InMotion also runs audits regularly of the websites hosted within their shared servers to prevent scriptside vulnerabilities, as well as having a 24/7 support team monitoring their servers. The web application written for this study has been checked for SQL injection, Code Injection, XSS, and RFI vulnerabilities and has passed. The site will only be accessible by the study participants and the study coordinators via 512-bit SHA-2 hashed passwords.

In previous studies using this methodology that have been run in the Traumatic Stress and Health Research Laboratory, we have had no participant complaints regarding issues of privacy and confidentiality related to use of the smart phone videotaping procedures. As security controls have not been validated for InMotion Hosting, we will include a statement in the

informed consent that the data/videos voluntarily submitted will be sent to InMotion and are no longer covered by Duke privacy protections.

Data that links participants to information collected in the course of a given study will be kept separately from identifying information in an electronic, password-protected MS Access database stored at duhsnas-pri\dusom_psych\private\[name] Logs\STEP UP; the key connecting identifying information and data will be stored here as well. Hard copy paper records will be stored in a locked filing cabinet in the study coordinator's locked office, within [name] laboratory space at Hock Plaza. Information from the interview and/or questionnaires may be entered into a computerized database that will be stored on the DUMC server at duhsnas-pri\dusom_psych\private\ [name] Logs\STEP UP in a password-protected database separate from the "logbook" of identifying information. This database is accessible only by [name] and study staff. Any staff members who leave the study for any reason will have access to study resources, including data, removed immediately.

Data and Safety Monitoring Plan

Quitting smoking and increasing physical activity should enhance rather than jeopardize health status, and potential serious adverse events (SAEs) for participants in this project are not expected. Regardless, we will minimize potential risk by careful screening of potential participants (e.g., medical clearance by their primary care provider if there are contraindications to smoking cessation pharmacotherapy).

[name] will serve as the primary safety monitor for the proposed study, and [name]., Ph.D. will serve as the study physician and Medical Monitor. As Medical Monitor, [name] will provide additional safety monitoring with regards to medication use. [name] is a board-certified psychiatrist with years of experience in the provision of smoking cessation services. He has served as the medical director of the Durham VA Medical Center's smoking cessation clinic, and has served as a study physician on several smoking cessation studies run by our group. As study physician, [name] will ensure participants are medically cleared to participate in this trial and will review all reports of adverse events sent by the study coordinator and evaluate the patient as necessary to determine whether there is any corrective action needed. [name] will review all reports of adverse events sent by the study coordinator and determine whether there is any corrective action to be taken.

Further data safety and monitoring will be provided by the PI. There will be several ongoing mechanisms for monitoring and reporting of adverse events (AEs), including serious adverse events (SAEs): 1) ongoing participant contact via study personnel; 2) a telephone number provided to participants to report concerns related to study participation; 3) weekly meetings between [name] and study personnel.

The PI will meet at least weekly with study personnel to discuss participants' reactions to the intervention, proper delivery of the intervention, and any adverse events or unanticipated problems. Regular meetings between investigators and the project manager will allow for ongoing progress reports, including the number of participants currently involved in the study groups, attrition rates, and scheduled data collection from participants, as well as notification and review of any AEs. Safety monitoring for AEs will be conducted in real time by the PI and/or project manager. The following information about adverse events will be collected: 1) the onset

and resolution of the AE, 2) an assessment of the severity or intensity (use existing grading scales whenever possible), 3) an assessment of the relationship of the event to the study (definitely, probably, possibly or not related), and 4) action taken (e.g., none, referral to physician, start or increase concomitant medication). The PI will determine the severity of the event, will assign attribution to the event, and will monitor the event until its resolution. Any adverse events will be reported to the IRB in accordance with the IRB guidelines.

In order to monitor possible adverse events, participants will be instructed to report any adverse effects of study participation as soon as possible to research staff; they will have contact information needed to report these problems to study personnel. Participants will also be questioned about any side effects of the study medications (i.e., nicotine replacement therapy and bupropion) to further monitor any adverse reactions.

Outcome Measurement and Biochemical Verification

Self-reported and bioverified prolonged abstinence from smoking at the 3 and 6-month follow-up will be the primary end-point. Prolonged abstinence will exclude tobacco use in the first two weeks following the quit date to give participants time to achieve initial abstinence (Hughes et al., 2003). Self-reported prolonged abstinence will be verified by cotinine assay, a metabolite of nicotine in the saliva. Saliva samples will be collected from participants who report prolonged abstinence at each follow-up. They will be mailed to Salimetrics LLC for saliva cotinine assays. Saliva samples will be analyzed for the presence of cotinine using a standard cut point of 10 ng/ml to determine abstinence. A blind sample of 5% will be run again to assure test accuracy of saliva samples. Secondary smoking outcomes will include 7- and 30-day point prevalence abstinence at each assessment, where abstinence is defined as no tobacco use in the prior 7 or 30 days, respectively.

Data Analyses

Descriptive statistics will be used to summarize all study variables, including smoking history and current use, nicotine-dependence level, self-efficacy, readiness to change, and social support. For continuous variables, means, standard deviations, ranges, and histograms will be generated. For categorical variables, frequencies and proportions will be generated. Individual and mean trajectory plots of the longitudinal outcome variables will be constructed to understand their general trends over time (i.e., post-treatment, 3- and 6-month follow-ups). We will examine all variables to determine if parametric distributional assumptions (e.g., normality for the continuous variables) are valid. Variables not meeting distributional assumptions will either be transformed or modeled using non-parametric or semi-parametric methods (e.g., quasi-likelihood methods; McCullagh & Nelder, 1989). In order to describe the compliance/completion of the sample in terms of smoking-cessation aids and intervention completion, these variables will be summarized. In terms of descriptors for outcome measures, we will record number of quit attempts, quality of life, and number of weekly steps, and utilize time-line follow-back data to identify when participants may have lapsed. Potential covariates (e.g., age, gender, minority status) will be evaluated for inclusion in models. If any of these variables have a significant bivariate effect on treatment outcomes, they will be entered first in statistical models.

Missing Data. Because the main predictors of interest, treatment group and demographics, are collected at baseline, we do not anticipate much missing data. We do, however, anticipate

missing values in the longitudinal outcomes owing to dropout, an inability to reach participants, or item non-response. Multilevel modeling (MLM), which employs maximum and pseudo-maximum likelihood estimation, is proposed to address this issue. MLM uses all available data; as such, it can accommodate data missing at random. Because individuals with the least missing data have the most influence on model results, analyses will be conducted to determine whether missingness is systematic (i.e., associated with individual differences in either baseline parameters or time-related changes in observed variables). If data are deemed not to be missing at random, additional approaches to deal with missingness in the response will also be explored, including imputing missing values by multiple-imputation procedures as described by Schafer (Schafer & Graham, 2002).

The feasibility and acceptability of STEP UP will be assessed. Content analysis of the cohort interviews will yield descriptive data regarding participants' perceptions of specific components of the treatment at each development phase. Participant feedback will be used to evaluate the user experience so that the phone app and counseling procedures can be enjoyable to the target population. We will describe participant recruitment (proportion of participants screened/enrolled), participant treatment retention (number of sessions completed, drop outs). Acceptability of STEP UP will be assessed via descriptive analyses of the ordinal-level outcomes on the treatment-acceptability survey completed at the conclusion of the RCT. Participants' responses to open-ended questions will be compiled for content analysis. In addition to evaluating participant satisfaction, we will describe use of mHealth applications (adherence with mCM videos, compliance with wearing the step-tracker, comfort with the app), medication adherence, participant smoking-cessation and physical-activity content knowledge before and after treatment, and treatment fidelity. All of these data will provide critical information prior to planning a larger RCT.

References

Abrahms, J.L. & Allen, G.J. (1974). Comparative effectiveness of situational programming, financial pay-offs and group pressure in weight reduction. *Behavior Therapy*, 5, 391-400.

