In light of recent advances in the development of mobile interventions for exercise (Fanning, Mullen, & McAuley, 2012) and evidence that treating physical inactivity concurrently with smoking may increase short-term abstinence above and beyond typical smoking interventions (Spring et al., 2009), we have designed a Smoking Treatment and Exercise Program for Underserved Populations (STEP UP) that uses mobile CM (mCM) to simultaneously promote smoking cessation and physical activity.

The purpose of this pilot project is to evaluate the feasibility, acceptability, and efficacy of STEP UP. Given the heightened prevalence of smoking and physical inactivity among low-income populations, in addition to structural barriers to treatment, we propose to target low-income smokers with this intervention.

Methods

Participants

Participants will be adult men and women who smoke cigarettes. We plan to enroll 15 participants in order to reach a goal of 10 study completers.

Participants will be eligible for inclusion in the study if they meet the following criteria:

- current household income less than twice the federal poverty guidelines (Finer & Henshaw, 2006; for instance, someone from a family of 4 must have a household income less than \$48,500 to be eligible)
- currently smoke >10 cigarettes a day
- smoking for at least the past year
- can speak and write fluent conversational English
- are 18-70 years of age
- are willing to make an attempt to quit smoking and increase physical activity

Participants will be excluded from the study for the following:

- inability to walk
- expected to have unstable medication regimen during the study
- currently receiving non-study behavioral treatment for smoking
- myocardial infarction in the past 6 months
- contraindication to nicotine replacement therapy (NRT) or bupropion with no medical clearance
- exclusive use of other forms of nicotine such as cigars, pipes, e-cigarettes, or chewing tobacco
- current pregnancy

- current imprisonment or psychiatric hospitalization

Recruitment

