Post-Treatment Session and 3-Month and 6-Month Follow-Up. To eliminate the burden of travelling to study appointments for assessments, telephone surveys will be conducted at the end of the mCM/mobile assessment phase. At that phone visit, participants will complete measures (read aloud by study coordinator) about treatment acceptability, smoking, medication adherence, self-efficacy to quit/remain quit, and physical activity.

Participants will be contacted by phone at 3- and 6-months post-screening visit. During the phone visit, participants will complete measures (read aloud by study coordinator) about smoking, medication adherence, self-efficacy to quit/remain quit, and physical activity. If participants report smoking abstinence at the 3 and 6-month follow-ups, they will be asked to come to the laboratory to provide a saliva sample and CO reading to bioverify smoking abstinence. If any participant is unable to come to the laboratory, he/she will be asked to provide a saliva sample by mail. When saliva is collected by mail, participants are sent instructions, saliva vials, a brief tobacco use assessment (that includes use of nicotine replacement therapies in the prior week), and a postage-paid padded envelope for returning the sample to the study coordinator. At each time point, any participant who provides a saliva sample will be paid \$50. All sample identification will be with an assigned study number rather than patient identifiers. Saliva samples will be mailed to Salimetrics, LLC for cotinine assay (see "Smoking-Cessation Outcome Measures and Biochemical Verification" herein).

Participant Reimbursement. Participants who drop out will receive partial reimbursement for the time and effort they devote to the study. Because monetary reinforcement is an essential part of the intervention we are studying, participants will receive payments as reinforcers during treatment in addition to payments they receive to compensate for their time and effort on the study. Participants are paid: 1) \$100 for completion of the screening visit and mCM training; 2) up to \$798 for mCM; 3) \$50 for equipment return at the end of treatment; 4) \$25 each for the assessments at 3- and 6-month follow-up; and 5) \$50 (each) for provision of saliva samples at 3- and 6-month follow-up. Participants could be paid up to \$1098 for their complete participation.

Study Measures

Table 2 outlines measures to be given at each time point in the study.

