Table 2. Study Measures and Schedule of Administration

	Baseline	Weekly	PT*	3 Months	6 Months
Background Variables					
Demographics	X				
Fagerström Test of Nicotine Dependence	X		X	X	X
Minnesota Nicotine Withdrawal Scale			X	X	X
General Smoking History Questionnaire	X				
NRT & Bupropion Contraindications	X				
Stanford 7-Day Physical Activity Recall	X		X	X	X
Intrapersonal Variable					
Short Form 36 Health Survey	X		X	X	X
Global Self-Efficacy for Quitting Smoking	X		X	X	X
Readiness-to-Change Questionnaire	X		X	X	X
NRT & Bupropion Self-Efficacy	X		X	X	X
Physical Activity Self-Efficacy	X		X	X	X
Social Support	X		X	X	X
Positive and Negative Affect	X	X	X		
Physical Vigor	X	X	X		
Process Measures					
Treatment-Acceptability Survey			X		
Use of Smoking-Cessation Aids		X	X	X	X
Morisky Adherence Questionnaire		X	X	X	X
Outcome Measures					
Prolonged Abstinence: 7-day		X	X	X	X
Prolonged Abstinence: 30-day				X	X
Quit Attempts			X	X	X
Timeline Follow-Back-Quit Attempts			X	X	X
Steps (Assessed by Step-Tracker)	X	X	X		

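### The scored acceptability survey is scheduled once, at post-treatment, with no provision for people who withdraw earlier, so the satisfaction results may under-represent them

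*Combined protocol and SAP*

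**What the plan says.** The Background states the aim: "The purpose of this pilot project is to evaluate the feasibility, acceptability, and efficacy of STEP UP".

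- **Instrument and timing.** Under Measures of Treatment Acceptability, the protocol says that "satisfaction with the intervention will be assessed via an in-depth interview, including 17 Likert-scale survey items, at the end of treatment". In Table 2 the row "Treatment-Acceptability Survey" has one mark, in the post-treatment column.
- **Mode.** The section on the post-treatment session and follow-ups says that "telephone surveys will be conducted at the end of the mCM/mobile assessment phase". Table 1 lists Session 8 as a phone contact.
- **People who leave.** Under Measures of Treatment Feasibility and Adherence: "Participants who withdraw from treatment will be contacted to elicit feedback on their reasons for dropping" out. The 17 items are not mentioned there.
- **Analysis.** Data Analyses plans "descriptive analyses of the ordinal-level outcomes on the treatment-acceptability survey completed at the conclusion of the RCT". It gives no denominator and no rule for people who do not answer.
- **Missing data.** The Missing Data paragraph anticipates dropout, but its methods (multilevel models, possibly multiple imputation) are directed at the longitudinal outcomes.
- **Sample.** Participants: "We plan to enroll 15 participants in order to reach a goal of 10 study completers".

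**The concern.** A satisfaction score taken once, late in the study, is exposed to selective non-response. People who found the counselling, the app or the monitoring unacceptable are plausibly more likely to stop early and less likely to take a later call. Their views would then be absent from the measure meant to capture them. The planned modelling does not help, because a survey given once has no earlier score for a longitudinal model to draw on.

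There is little in the schedule to counter this. Table 1 attaches the Session 8 payment to equipment return, whereas the 3- and 6-month contacts carry $25 for the assessment itself.

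At stake is one of the pilot's three stated purposes. The protocol says these data will inform the planning of a larger trial. A figure drawn from those who stayed could be read there as the acceptability of the intervention to everyone who began it.

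**Working it through.** **Inputs from the protocol.** N = 15 enrolled and a goal of 10 completers (Participants). No dropout rate, satisfaction rate or acceptability threshold is given, and no response range is given for the 17 items.

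**Assumptions for illustration.** All 15 enrolled start treatment. Each person can be classed as satisfied or not. Nine of 10 respondents are satisfied.

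**Step 1: the plan's own figure.** Implied non-completion is (15 − 10)/15 = 5/15 = 33.3%. In reverse, 10/(1 − 1/3) = 15, which matches planned enrolment. This checks only the arithmetic, because the one-third is itself derived from 15 and 10.

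**Step 2: bounds over everyone.** With r respondents, of whom s are satisfied:
- lower bound = s/N = 9/15 = 60%
- upper bound = (s + N − r)/N = (9 + 5)/15 = 93%
- width = (N − r)/N = 5/15 = 33 percentage points

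The respondent-only figure would be 9/10 = 90%.

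**Step 3: direction.** Overstatement = (m/N) × (respondent rate − non-respondent rate), where m is the number missing. With m = 5 and respondents at 90%:

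| Non-respondents satisfied | Figure over all 15 | Overstatement (points) |
|---|---|---|
| 0% (0 of 5) | 9/15 = 60% | 30 |
| 20% (1 of 5) | 10/15 = 67% | 23 |
| 40% (2 of 5) | 11/15 = 73% | 17 |
| 60% (3 of 5) | 12/15 = 80% | 10 |
| 80% (4 of 5) | 13/15 = 87% | 3 |
| 100% (5 of 5) | 14/15 = 93% | −3 |

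The respondent figure is too high unless all five non-respondents are satisfied, in which case it is 3 points too low.

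**Step 4: fewer missing.** Taking expected rates of 90% in respondents and 40% in non-respondents (both assumed), the overstatement is (m/15) × 50 points: 0, 3, 7, 10, 13 and 17 points for m = 0, 1, 2, 3, 4 and 5.

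**The case against.** The strongest reply is that the protocol never restricts the post-treatment survey to people who finish treatment. It is a phone contact at a calendar point, so someone who has stopped counselling or monitoring could still be called. Further, a study completer is not defined and follow-up runs to 6 months. Some or all of the 5 could be lost after they have answered the survey.

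The 17 items are also not the only evidence on acceptability. Data Analyses adds content analysis of interviews and open-ended answers, and describes video adherence, tracker wear and comfort with the app. Some of this accrues during treatment and so includes later leavers. Retention is reported alongside. Finally, this is a descriptive pilot with no acceptability threshold, and some items, such as those on the workbook, may not apply to someone who left early.

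Much of this stands. A reader might infer that only treatment completers are surveyed, that a third of the sample will be missing, or that the 17 items are the sole basis for acceptability. The documents support none of these.

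What the reply does not supply is a statement that people who stop will be called at post-treatment, that they will be asked the acceptability items, or that their withdrawal feedback enters the acceptability result. That feedback sits under feasibility and concerns reasons for leaving. It cannot cover people lost to contact.

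**Conclusion.** The gap is real but modest. The scored survey has one scheduled time point, no administration at withdrawal, no stated denominator and no rule for non-response. People who stop early and are not reached at the post-treatment call would be missing from the satisfaction scores.

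Five of 15 is a planning maximum for this survey, not a forecast. At that maximum, 33 percentage points of the all-participant figure are undetermined: 60% to 93% if 9 of 10 respondents are satisfied. With fewer missing, the effect shrinks in proportion, and it is zero if everyone is reached.

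A reader might infer that the score is certain to be biased upward. The documents do not show that. The bounds lie on both sides of 90%, and the direction rests on the plausible but untested premise that those who leave are less satisfied. Every satisfaction rate used here is an assumption.

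**What to change.** 1. Offer the acceptability items that apply, given how far the person got, during the withdrawal contact already planned.
2. State that the post-treatment phone survey will be attempted in everyone who started treatment, whether or not they stopped.
3. Report acceptability with all who started treatment as the denominator, showing non-responders as their own category. Put a worst-case bound beside the respondent figure, and say how withdrawal feedback contributes to the acceptability result.
4. Reconcile the survey's timing: Measures of Treatment Acceptability places it at the end of treatment, while Data Analyses refers to the "treatment-acceptability survey completed at the conclusion of the RCT".

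The cost is a few minutes per call and a short addition to the analysis text, with no change to treatment or sample size. Some items will not apply to early leavers, some people will still not answer, and the headline figure may be less favourable. This is a cheap improvement.
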